2.4.3.2 Compliance

A given administration will be considered noncompliant if the patient did not take the planned dose of treatment as required by the protocol. No imputation will be made for patients with missing or incomplete data.

Percentage of compliance for SC IMP will be defined as the number of administrations the patient was compliant divided by the total number of administrations the patient was planned to take on or before the last dose date during the DB treatment period.

Percentage of compliance for oral IMP compliance rate will be defined as the total number of days patient with partial or complete oral IMP intake divided by total number of days between the first oral IMP intake date and day prior to rescue therapy start date or EOT date which is earlier.

Treatment compliance percentages will be summarized descriptively as quantitative variables (number, mean, SD, median, minimum, and maximum). The percentage of patients whose compliance is <80% will be summarized.

Cases of overdose (administering two or more doses of sarilumab or its matching placebo in less than 11 calendar days) will constitute AESI and will be listed as such. More generally, dosing irregularities will be listed in [Section 2.2.1](#).

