6 STUDY DESIGN

6.1 DESCRIPTION OF THE STUDY

This is a multicenter, randomized, double-blind, placebo-controlled 52-week Phase 3 study with a 24-week post-treatment follow up phase, evaluating the efficacy and safety of sarilumab in patients with GCA.

Approximately 360 patients with GCA (new onset or refractory [eg, disease relapse] GCA) who meet the entry criteria will be randomized to 4 parallel treatment groups with sarilumab 200 mg q2w, 150 mg q2w, or placebo q2w plus 26-week prednisone taper, or placebo q2w with 52-week standardized prednisone taper at a ratio of 2:1:1:2 as described below. The protocol will aim to enroll at least 30% of new onset patients, therefore, the Sponsor will reserve the possibility to cap enrolment of refractory patients to $\leq 70\%$ of total patients randomized. Randomization will be stratified by the starting dose of prednisone at baseline (<30 mg/day or ≥ 30 mg/day).

- Treatment Group A: sarilumab 200 mg q2w with a 26-week taper of CS.
- Treatment Group B: sarilumab 150 mg q2w with a 26-week taper of CS.
- Treatment Group C: sarilumab matching placebo q2w with a 26-week taper of CS.
- Treatment Group D: sarilumab matching placebo q2w with a 52-week taper of CS.

It is important to optimize CS treatment prior to randomization to minimize the risk of adverse sequelae from GCA. Patients will be dosed with prednisone between 20 to 60 mg/day at the time of randomization (baseline) and initiate taper according to the protocol defined schedule. Patients will be initiated on a standardized taper of prednisone from the time of randomization. The taper will initially be open label; patients will have between 1 to 7 weeks to taper prednisone dose to 20 mg/day following randomization.

The further tapering of prednisone once a dose of 20 mg/day is achieved will be done in a blinded manner. To achieve the appropriate daily dose during this phase, patient will receive a combination of prednisone and/or placebo to prednisone depending on the assigned treatment group and associated taper regimen.

The total tapering period (open label plus double blind prednisone) will be between 46 weeks to 52 weeks depending on the initial prednisone dose at randomization.

At each site visit, the patient's disease will be assessed to determine whether the patient can adhere to the protocol defined prednisone taper schedule.

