8 STUDY TREATMENTS

8.1 INVESTIGATIONAL MEDICINAL PRODUCT(S)

Details of IMPs are provided in [Table 1](#).

There are 2 IMPs to be administered in this study:

- Sarilumab or sarilumab matching placebo
- Prednisone or prednisone matching placebo

In order to differentiate these 2 IMPs, sarilumab and sarilumab matching placebo are named as SC IMP, prednisone and prednisone matching placebo are named as oral IMP.

Table 1 - Summary of investigational medicinal products

	Name of IMP	Pharmaceutical forms	Dose of drug per administration	Route and method of administration	Treatment duration
Double blind phase of sarilumab	Sarilumab	Single-use 1.14 mL prefilled glass syringes containing 175 mg/mL (200 mg) & Single-use 1.14 mL prefilled glass syringes containing 131.6 mg/ml (150 mg)	Sarilumab 200 mg & Sarilumab 150 mg	Subcutaneous	Entire 52 week treatment period
Double blind phase of sarilumab	Sarilumab matching placebo	Placebo solution for injection	Matching placebo	Subcutaneous	Entire 52 week treatment period
Open label CS taper phase	Prednisone	5 mg & 20 mg Tablets	Refer to standard CS taper regimen Appendix B	Oral administration	1 to 7 weeks OL CS taper phase, depending on starting dose (refer to Appendix B)
Double blind CS taper phase	Prednisone	1 mg & 5 mg Capsules	Refer to standard CS taper regimen Appendix B	Oral administration	45 weeks DB CS taper phase (refer to Appendix B)

	Name of IMP	Pharmaceutical forms	Dose of drug per administration	Route and method of administration	Treatment duration
Double blind CS taper phase	Prednisone matching placebo	Capsules	Refer to standard CS taper regimen Appendix B	Oral administration	45 weeks DB CS taper phase (refer to Appendix B)
CS = corticosteroid; DB = double blind; IMP = investigational medicinal product; OL = open label.					

8.1.1 Sarilumab or matching placebo:

Additional detail regarding the method of administration

Formulation:

Sarilumab drug product will be provided as single-use 1.14 mL prefilled syringe (PFS) containing 131.6 mg/mL (150 mg), 175 mg/mL (200 mg) of sarilumab or placebo solution for SC injection. No preparation at the clinical site is required.

Route of Administration:

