- Open-label phase (from 1 to 7 weeks): all patients will go through this phase in order to have the prednisone dose tapered down to 20 mg/day. Patients may start at 60 mg/day or any of the incremental dosages: 50 mg/day, 40 mg/day, 35 mg/day, 30 mg/day, 25 mg/day, or 20 mg/day. Patients will follow the tapering schedule as per [Appendix B](#), completing the open-label phase and transitioning to the blinded phase of tapering after 1 to 7 weeks, depending on the prednisone dose at baseline (ie, patients starting on 35 mg/day will transition to the double-blind phase of tapering quicker than patients starting on 50 mg/day).
- Blinded phase (45 weeks): Over encapsulated prednisone and/or matching placebo will be used to maintain blinding of the taper regimen regardless of regimens that the patient is assigned to.

During the prednisone taper blinded phase, patients will be supplied with weekly blister packs which will be numbered and will clearly indicate the number of tablets to be taken per day. It is important that the blister packs be used in the correct order and that 7 days of dosing from each blister be taken by the patient before starting the next blister pack. If a patient visit is scheduled before the patient has used 7 days of a particular weekly blister pack, then this blister pack should be returned to the patient so that the patient can complete the remaining days of dosing with that blister pack before starting the next sequentially numbered blister pack. If doses have been missed, it is not necessary for patients to use the missed capsules before progressing to their next blister packs.

During the blinded taper, the daily encapsulated dose may contain prednisone, placebo, or a combination of the two. The number of capsules to be taken each day will vary but will not be indicative of the dosage of prednisone. The number of capsules to be taken daily may increase or decrease during the tapering schedule but will not exceed 5 capsules per day.

Refer to [Appendix B](#) for detailed standardized CS-taper regimen during the double-blind study treatment period.

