10.2.2.4 Visit 12/End of Treatment (Day 365 ±3, Week 52)

- Call IRT to register visit.
- Administer PRO questionnaires (EQ-5D, FACIT-Fatigue, SF-36v2, HAQ-DI).

Note: PRO questionnaires should be completed prior to any significant interaction with the study team and prior to any physical examination or sampling.
- Review of concomitant medication.
- Review last visit patient diary.
- Measure vital signs (including systolic and diastolic BP [mmHg], and HR [beats per minute], body temperature [°C]).
- Body weight (kg).
- GCA clinical assessments (including disease flare).
- Complete physician global assessment (MD-VAS).
- Inquire about AEs/SAEs.
- Tuberculosis assessment.
- Full physical examination.
- GTI Assessment.
- Bone density assessment by DXA (-2 week time window is allowed).

- Perform blood sampling (fasting) for the following tests:
 - Hematology and chemistry.
 - ANA.
 - Fasting lipids, fasting glucose and fasting insulin.
 - HbA1c.
 - CRP and ESR.
 - Serum sarilumab and ADA.
 - Biomarkers IL-6, sIL-6R.
 - Serum and plasma sampling for circulating protein (for consented patients only).
- Perform urine pregnancy test (for WOCBP).
- Schedule an appointment for Visit 13.

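### The oral IMP compliance denominator runs to the EOT date, so for starting doses below 60 mg it counts 1 to 6 weeks with no scheduled oral dose as missed

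*SAP*

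**What the plan says.** SAP 2.4.3.2 (Compliance) defines oral IMP compliance as a ratio of days. The numerator is the "total number of days patient with partial or complete oral IMP intake". The denominator is the "total number of days between the first oral IMP intake date and day prior to rescue therapy start date or EOT date", whichever comes first. The section then adds: "The percentage of patients whose compliance is <80% will be summarized".

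Protocol 8.1 fixes what is counted: "prednisone and prednisone matching placebo are named as oral IMP". Open-label prednisone is therefore included, and first intake is normally Day 1. Protocol 8.1.2 gives an open-label phase of 1 to 7 weeks, depending on starting dose, and a blinded phase of 45 weeks for everyone. Protocol 6.1 says that the total tapering period "will be between 46 weeks to 52 weeks depending on the initial prednisone dose at randomization". The Appendix B tables agree: after the last scheduled week, the remaining weeks up to Week 51 are marked as having no prednisone dosing. These begin at Week 46 for a 20 mg start and at Week 51 for a 50 mg start; a 60 mg start has none. The end-of-treatment visit is Visit 12, Day 365 ±3 (Protocol 10.2.2.4).

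The SC IMP formula in the same SAP section behaves differently. Its denominator counts only administrations planned on or before the last dose date.

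**The concern.** The oral formula counts calendar days, not scheduled days, and its end point can fall after the oral schedule has finished. For any start below 60 mg, the reported percentage is then pulled down by an amount set by the taper calendar, not by what the patient took. This also sits badly with the opening sentence of SAP 2.4.3.2, which ties non-compliance to not taking a planned dose: on these days none is planned.

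Two reported results are affected: the summary statistics for oral compliance and the count below 80%. The count would mix real non-compliance with starting dose. Rescued and unrescued patients would also not be comparable. Rescue before the schedule ends cuts the denominator before the undosed weeks, so a rescued patient can still reach 100%, while an unrescued completer who started below 60 mg cannot.

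**Working it through.** **Inputs.** Open-label weeks by starting dose (Protocol 8.1.2 and Appendix B): 1, 2, 3, 4, 5, 6 and 7 for 20, 25, 30, 35, 40, 50 and 60 mg. Blinded weeks: 45. EOT: Day 365 ±3. Flag: below 80%.

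**Plan's own figure.** Total taper = open-label weeks + 45, so 1 + 45 = 46 and 7 + 45 = 52 weeks. This reproduces the range in Protocol 6.1.

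**Ceiling.** Scheduled days = 7 × (open-label weeks + 45). With every scheduled dose taken, no rescue and EOT on Day 365, the denominator is 364 as a date difference (365 − 1). Ceiling = scheduled days / 364.

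**Misflagged range.** On 364 days, 291/364 = 79.9% and 292/364 = 80.2%, so anyone with 291 or fewer intake days is flagged. True compliance = intake days / scheduled days. A patient is wrongly flagged if intake days are at least 80% of scheduled days but no more than 291.

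| Start (mg) | Scheduled weeks | Scheduled days | Ceiling on 364 days | Intake days wrongly flagged | True compliance of those patients |
|---|---|---|---|---|---|
| 20 | 46 | 322 | 88.5% | 258–291 | 80.1%–90.4% |
| 25 | 47 | 329 | 90.4% | 264–291 | 80.2%–88.4% |
| 30 | 48 | 336 | 92.3% | 269–291 | 80.1%–86.6% |
| 35 | 49 | 343 | 94.2% | 275–291 | 80.2%–84.8% |
| 40 | 50 | 350 | 96.2% | 280–291 | 80.0%–83.1% |
| 50 | 51 | 357 | 98.1% | 286–291 | 80.1%–81.5% |
| 60 | 52 | 364 | 100% | none | – |

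Counting inclusively (365 days) leaves the cut at 291 days, since 292/365 = 80.0%, and lowers the 20 mg ceiling to 322/365 = 88.2%.

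**Visit window.** The denominator can run from 361 (Day 362, date difference) to 368 (Day 368, inclusive). The 20 mg ceiling then runs from 322/361 = 89.2% to 322/368 = 87.5%. The cuts move too: a 20 mg starter with 290 of 322 days (90.1% true) scores 290/364 = 79.7% and is flagged, but 290/361 = 80.3% and is not.

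**Can a fully compliant patient be flagged?** For a 20 mg start, 322/0.80 = 402.5, so the denominator would have to reach 403 days. That is 403 − 365 = 38 days, over five weeks, past Day 365. Within the visit window it cannot happen.

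**Who is exposed.** The patient must start below 60 mg, have no rescue before the last scheduled oral day, and have EOT after that day. SAP 1.3 says about 36 of 83 patients could complete 52 weeks. Under the discontinuation plan, EOT is no later than 13 October 2020. Going back 322 days gives 26 November 2019 as about the latest randomization date for an affected 20 mg starter; going back 357 days gives 22 October 2019 for a 50 mg starter.

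**The case against.** The strongest reply is that SAP 2.4.3.2 never defines EOT date. SAP 2.5.3, dealing with a missing end-of-treatment date, takes the last SC administration as the end of treatment for duration. Read that way for oral IMP, the denominator stops at the last oral dose and the gap disappears. Read as the last SC dose at Week 50, it only shrinks: the 20 mg ceiling is 322/350 = 92.0%. The uncertainty is real, but nothing in the SAP settles it in favour of the last oral dose. Elsewhere EOT mostly means the visit: the bone density rules in SAP 2.1.3.2, the cohort definition in SAP 2.3.1, and the flow chart in SAP Appendix A. If the last oral dose were meant, the rescue clause would add little, because under Protocol 8.2 a patient who flares stops the taper and cannot return to it after rescue.

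It is also fair to say that the consequences are limited. A reader might infer that the primary endpoint is affected, since taper adherence is one of its components. It is not: SAP 2.1.3.1 defines that component by absence of rescue and a limit on excess prednisone, and does not use this percentage. No analysis population depends on it, and no test is attached. Cumulative corticosteroid dose (SAP 2.4.4.2) is built from intake days directly and has no such denominator. The ceilings do separate the randomization strata (at most 90.4% below 30 mg, at least 92.3% otherwise), but compliance is summarized by treatment group and no subgroup analyses are planned.

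**Conclusion.** The rule is wrong as written, with modest consequences. Taking EOT date as the Week 52 visit, an unrescued completer who took every scheduled oral dose scores at most 88.5% to 98.1% for starts of 20 to 50 mg (364 days), and the shortfall reflects only the taper calendar.

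A reader might infer that fully compliant patients end up in the below-80% count. The figures do not support that: within the visit window the lowest attainable value is 87.5%. Those misflagged did miss doses but took at least 80% of what was scheduled, up to about 90.4% for a 20 mg start and about 81.5% for a 50 mg start, with the exact cut moving with the visit day.

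The effect is confined to a descriptive summary and to unrescued patients whose EOT falls after their last scheduled oral day, mainly among the roughly 36 who could reach Week 52. How many that is, and whether anyone is actually misflagged, cannot be worked out, because the documents give no starting-dose distribution.

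**What to change.** Define the oral denominator as the days from first oral intake to the earliest of three dates: the day before rescue starts, the EOT date, and the last day on which Appendix B schedules oral IMP, active or placebo, for the patient's starting dose (open-label weeks plus 45 blinded weeks). Apply the 80% cut on that basis, and state what EOT date means and whether both end days are counted. Every fully compliant patient then scores 100%, and a 20 mg starter who completes the schedule is flagged below 258 of 322 days instead of below 292. The cost is one sentence in SAP 2.4.3.2 and a lookup by starting dose in the program. No new data are needed.

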2.4.4 Analyses of efficacy endpoints

The analyses of efficacy endpoints will be descriptive in nature. For majority of the efficacy endpoints, only descriptive summary statistics will be provided by 4 treatment groups. For the primary and some selected important secondary endpoints, summary statistics and formal statistical tests on between group comparisons (with 95% CI and p-value) will be provided for the 2 combined treatment groups (ie, 2 sarilumab groups combined versus 2 placebo groups combined); no formal comparisons will be performed between 4 individual treatment groups due to the small sample size.

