6.5 DISCUSSION OF STUDY DESIGN AND CHOICE OF CONTROL GROUPS

EFC15068 has been designed as a 52-week, double-blind, placebo-controlled, randomized, comparator study with a 24-week posttreatment follow up phase, to evaluate the efficacy and safety of sarilumab in patients with GCA. The 52-week study treatment duration reflects the standard duration of corticosteroid therapy required to ensure sustained remission for patients with GCA (hence, the primary endpoint of sustained remission is at Week 52). This duration of treatment is consistent with that in published interventional studies in GCA (11, 18).

Approximately 360 patients who have either newly diagnosed GCA or have refractory active GCA, will be enrolled and randomized into 4 different arms to receive either sarilumab 200 mg q2w with 26-week prednisone taper (Group A) or sarilumab 150 mg q2w (Group B) with 26-week prednisone taper or sarilumab matching placebo with prednisone taper periods of either 26 weeks (Group C) or 52 weeks (Group D) in the ratio of 2:1:1:2.

The 26-week taper is selected to demonstrate that sarilumab can enable patients to taper off CS earlier rather than the usual prolonged taper of 52 weeks with CS alone. The ability to taper off of CS rapidly (26 weeks taper period as opposed to the usual tapering regimen of a year or more) while maintaining disease remission would represent an important clinically meaningful benefit. The 52-week taper mimicks the usual care with CS and serves as a calibrator arm. Therefore, the primary comparison will be between Group A (sarilumab 200 mg q2w) and Group C (placebo sarilumab) where a 26 week taper of CS regimen will be used in both arms. Group B will evaluate a second dose of sarilumab (150 mg q2w) also with a 26 week taper of CS. Group D will evaluate the effect of placebo sarilumab with a 52-week taper of CS that reflects usual care, and will serve as a calibrator for further benefit risk assessment.

The Weeks 12 to 52 period assesses the “sustainability” of the remission that should be achieved by Week 12 as this is the anticipated timepoint where most patients should have achieved remission in usual care with steroids. After completion of the 52-week, double-blind, placebo-controlled treatment period, patients will be followed for another 24 weeks to assess the durability of the treatment response.

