1.2 OBJECTIVES

1.2.1 Primary objectives

To evaluate the efficacy of sarilumab in patients with GCA as assessed by the proportion of patients with sustained remission at Week 52 for sarilumab compared to placebo, in combination with a 26-week CS tapering course.

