2.4.4.1 Analysis of primary and additional efficacy endpoint(s)

The analysis of primary endpoint of sustained remission at Week 52 will be limited to the cohort of patients who had an opportunity to complete the 52-week treatment period (i.e., Week 52 Analysis set).

The proportion of patients achieving sustained remission at Week 52 will be summarized using counts and percentages by the 4 treatment groups. In addition, the treatment effects between the combined sarilumab (group A+B) group and the combined placebo group (Group C+D) will be compared using a Cochran-Mantel-Haenszel (CMH) test stratified by prednisone dose at baseline (<30 mg/day or ≥30 mg/day).

The additional endpoint of sustained remission at Week 24 will be analyzed in the same fashion in the ITT population.

Sensitivity analysis excluding acute phase reactants:

Sensitivity analysis will be performed for the primary endpoint by removing the acute phase reactants (CRP and ESR) from the definition to mitigate against the possibility of biasing the results due to the known PD effect of sarilumab on acute phase reactants.

Patients achieving sustained remission at Week 52 (or Week 24) excluding acute phase reactants is defined by having met all of the following parameters:

- Achievement of disease remission not later than Week 12. **Disease remission** is defined as resolution of signs and symptoms of GCA.
AND
- Absence of disease flare from Week 12 through Week 52 (or Week 24). **Flare** is defined as recurrence of signs and symptoms attributable to active GCA plus an increase in CS dose due to GCA.
AND
- Successful adherence to the prednisone taper from Week 12 through Week 52 (or Week 24).

The sensitivity analysis will be performed in the same fashion as for the primary endpoint. Descriptive statistics (i.e., counts and percentages) will be provided for the three individual components.

Subgroup analyses:

No subgroup analyses will be performed due to the small sample size.

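### The only planned between-group analysis of sustained remission pools the 26-week and 52-week taper controls, so no difference or interval is specified for the same-taper contrast named in the primary objective

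*SAP*

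**What the plan says.** SAP 1.2.1 carries the primary objective over from the protocol unchanged: "sustained remission at Week 52 for sarilumab compared to placebo, in combination with a 26-week CS tapering course". Protocol 6.5 turns this into a contrast, "the primary comparison will be between Group A (sarilumab 200 mg q2w) and Group C (placebo sarilumab", on the ground that both arms share the 26-week taper. Protocol 11.4.2.1 names the same comparison, and 11.4.2.3 places it first in the testing order. Of Group D, protocol 6.5 says: "The 52-week taper mimicks the usual care with CS and serves as a calibrator arm".

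The SAP was written after the sponsor stopped the study with 83 of 360 planned patients randomized. Its between-group contrast is "2 sarilumab groups combined versus 2 placebo groups combined" (SAP 2.4.4). For sustained remission at Week 52, SAP 2.4.4.1 makes this a CMH test of A+B against C+D within strata of baseline prednisone dose. The added Week 24 endpoint and the sensitivity analysis without acute phase reactants are handled in the same way. The results for each arm "will be summarized using counts and percentages by the 4 treatment groups". SAP 2.4.4 adds that "no formal comparisons will be performed between 4 individual treatment groups due to the small sample size". Appendix C repeats the rule: the stratified test for combined groups, description otherwise. SAP 1.6 lists the pooling among the changes from the protocol, and SAP 1.6 and 2.4.4.3 make all p-values nominal.

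**The concern.** Groups A, B and C all follow the 26-week taper and only Group D follows the 52-week taper. A+B versus C+D therefore compares patients who differ in drug and, for most of the controls, in background steroid as well. The stated objective holds the taper fixed.

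The steroid gap is plain at Week 24, the time point at which all 83 patients can be analysed. In protocol Appendix B, every starting-dose column of the 52-week regimen stands at 6 or 7 mg/day at Week 24. Every column of the 26-week regimen stands at 1 mg/day or placebo.

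If Groups C and D differ in remission, the pooled difference is not an estimate of what the objective asks for, and the plan contains no between-group estimate that is. A reader of the study report could take the pooled difference as the answer to the primary objective.

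**Working it through.** **Inputs.** SAP Table 1 gives rates of A 54%, B 50%, C 14%, D 18%, A+B 53% and C+D 17%, and sizes of A 28, B 14, C 14, D 27, A+B 42 and C+D 41. The assumed rates come from the Week 52 planning assumptions; SAP 1.3 applies them to Week 24. The Week 52 Analysis set has 36 patients, with no split by arm given. We assume 12/6/6/12 from the 2:1:1:2 ratio.

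**Formula.** Two-sided chi-square, pooled variance under the null:

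power = Φ[(|p1 − p2| − z·SE0)/SE1]

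SE0 = √[p̄(1 − p̄)(1/n1 + 1/n2)], SE1 = √[p1(1 − p1)/n1 + p2(1 − p2)/n2]

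Approximate 95% interval: (p1 − p2) ± 1.96·SE1.

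**Reproducing the plan's figure (A+B vs C+D, Week 24).** p̄ = (42×0.53 + 41×0.17)/83 = 0.352; SE0 = 0.1049; SE1 = 0.0968. At 0.05: (0.36 − 1.96×0.1049)/0.0968 = 1.60, power 94.5%. At 0.01: 82.3%. Both match Table 1, and all ten powers in that table reproduce to within 0.1 point.

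**Same-taper contrast (A+B vs C, Week 24).** p̄ = (42×0.53 + 14×0.14)/56 = 0.4325; SE0 = 0.1529; SE1 = 0.1205. At 0.05: (0.39 − 1.96×0.1529)/0.1205 = 0.75, power 77.3%. Half-width 1.96×0.1205 = 24 points, against 1.96×0.0968 = 19 points pooled.

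| Contrast | n | Difference (points) | Approx. 95% CI | Power at 0.05 |
|---|---|---|---|---|
| Week 24, A+B vs C+D (planned) | 42 vs 41 | 36 | 17 to 55 | 94.5% |
| Week 24, A+B vs C | 42 vs 14 | 39 | 15 to 63 | 77.3% |
| Week 24, A vs C | 28 vs 14 | 40 | 14 to 66 | 74.0% |
| Week 52, A+B vs C+D (planned) | 18 vs 18 | 36 | 7 to 65 | 63% |
| Week 52, A+B vs C | 18 vs 6 | 39 | 3 to 75 | 36% |
| Week 52, A vs C | 12 vs 6 | 40 | 0 to 80 | 34% |

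These normal-approximation intervals are rough with 6 to 14 controls and are shown for scale only.

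**Dependence on Group D.** The pooled control rate is (14×0.14 + 27×pD)/41. The size-weighted sarilumab rate is (28×0.54 + 14×0.50)/42 = 52.7%. The same-taper difference is 52.7 − 14 = 38.7 points whatever pD is.

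| Group D rate | Pooled control rate | Pooled difference (points) |
|---|---|---|
| 14% (assumed) | 14.0% | 38.7 |
| 18% (SAP) | 16.6% | 36.0 |
| 25% (assumed) | 21.2% | 31.4 |
| 35% (assumed) | 27.8% | 24.8 |

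**The case against.** Much of the case for the plan stands.

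- **The change is open and reasoned.** SAP 1.6 lists the pooling, ties it to early termination and makes every result descriptive. A reader might infer that the switch was hidden; the documents show that it was not.
- **Arm-level results are reported.** A reader might infer that the objective cannot be addressed at all. That goes too far, because a crude same-taper difference can be worked out from the planned counts. What the plan lacks is a specified difference, an interval, or any estimate adjusted for the prednisone stratum.
- **Group D is more than a calibrator.** The secondary objectives cover either taper, and protocol 11.4.2.3 tests both doses against Group D on the primary endpoint. Using Group D as a comparator is legitimate, but it does not isolate the primary objective.
- **The numbers are small.** SAP 2.4.4 gives this as the reason for no formal comparison among the four individual groups. It is a fair reason not to test. It is weaker against estimation, and A+B vs C still pools the sarilumab arms. Table 1 itself shows 74.0% power at 0.05 for A vs C, a comparison the SAP does not run.
- **Week 52 would be fragile.** With about 6 controls at 14%, 0.84 responders are expected and the chance of none is 0.86⁶, about 40%. A stratified test there would be unreliable. This argues for intervals only, and against replacing the pooled test.

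**Conclusion.** The mismatch is real and modest. The objective fixes the taper, about two thirds of the pooled controls are on a different one, and no passage says that the pooled contrast departs from the objective or why the 52-week arm belongs in its control.

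At the SAP's rates the gap is about 3 points, well inside half-widths of 19 to 24 points at Week 24. A reader might infer that pooling flatters sarilumab. Under the documents' assumption that Group D does better than Group C (18% vs 14%), it does the opposite and shrinks the apparent benefit. A reader might also take it as established that steroid raises Group D's Week 24 remission rate. Appendix B shows the dose gap, but the documents do not quantify its effect on remission. The 25% and 35% rows are therefore our assumptions, chosen to show the range.

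Nor is A+B vs C the only contrast that holds the taper constant. A vs C and B vs C do so too, and A vs C is the protocol's own primary comparison. The Week 52 figures rest on the assumed 12/6/6/12 split.

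**What to change.** In SAP 2.4.4.1, keep the pooled stratified test as planned. Beside it add, as estimation only, risk differences with score or exact 95% intervals for A vs C and for A+B vs C, at Week 24 (ITT) and Week 52 (Week 52 Analysis set). State that these contrasts match the primary objective and that the pooled contrast mixes taper lengths. Carry the same wording into Appendix C.

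The cost is four extra estimates from data already planned, with no new p-values and no change to multiplicity. The intervals will be wider. For A+B vs C the half-width is about 24 points against 19 pooled at Week 24, and about 36 against 29 at Week 52 under the assumed split. With about 6 Week 52 controls those estimates will be very imprecise, and the report should say so.
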